4.4.2 Operative Procedures

The surgical process is to follow site standard of care.

Data collected during the operative procedure of the Subject is listed in Table 2.

Table 2: Operative Data Collection

| Form 3—Surgical Evaluation & Details | |
|---|--|
| Evaluation | Details of Evaluation |
| Imaging Evaluation | Baseline MRI and Standing Alignment X-Ray dates. |
| Standing Alignment | Patient's standing alignment. |
| Bone Marrow Edema Location | Surgeon must indicate locations of bone marrow edema on MRI. |
| Surgical Procedure Details | Description of Subject's operative procedure including such items as findings and treatments, operative times and diagnoses. |
| Adverse Event (if applicable) | Description of adverse events occurring during the operative procedure, if applicable . |

4.4.3 Postoperative Procedures

Immediate post-operative management is at the discretion of the surgeon and support staff and should follow each Site's standard of care.

Data collection for this study will occur post-operatively at 6 weeks, 3 months, 6 months, 1 year, 2 years, 3 years, 4 years and 5 years. The post-operative visit data listed in Table 3 must be collected for each enrolled Subject either in person or by email, mail or telephone.

Table 3: Postoperative Data Collection

| Form 4—Post-Operative Evaluation | |
|---|---|
| Evaluation | Details of Evaluation |
| VAS—Knee Pain | |
| Medications | |
| Surgical/Non-Surgical Procedures | Each of the questionnaires should be completed by the Subject. It typically takes 5-10 minutes per questionnaire to complete. |
| Work/Disability Status | |
| IKDC | |
| VR-12 Health Survey | |
| Adverse Event (if applicable) | 
Only AEs which are possibly or definitely related to the device or procedure will be reported to the sponsor.
 
Serious AEs must be reported as soon as possible and within 24 hours after the investigator first learns of the event. The Sponsor is subsequently responsible for reporting as required.
 
See Adverse Event Reporting in Section 5.
 |
| End of Study/Withdrawal | At any time during the study a Subject may withdraw. Subject withdrawal must be documented and provided to the Sponsor. |

4.5 Data Analysis

Please note that detailed patient demographic information (age, gender, location of defect, severity of symptoms, etc.) will be collected and analyzed to identify suitable candidates for SCP and to perform covariate analyses on the post-operative clinical outcomes for the study population.

5. Adverse Event Reporting

5.1 Adverse Events

An adverse event (AE) is defined as an untoward medical occurrence, unintended disease or injury, or untoward clinical signs (or change or worsening of a pre-existing medical condition) in a patient, which may or may not have an association with the

device. In addition an adverse device effect is defined as ‘any untoward and unintended response to a medical device’.

For this study, **only AEs which are possibly or definitely related to the device or procedure will be reported to the sponsor.** The determination whether the AE is related to the device or procedure will be based upon whether a causal relationship between the device or procedure and the AE is at least a reasonable possibility, i.e. the relationship cannot be ruled out. A causal relationship cannot be ruled out if, in the medical judgment of the investigator, the effect follows a reasonable temporal association with the use of the device and/or is confirmed by the improvement of the effect upon discontinuation of the clinical use of the device, and/or the effect is not reasonably explained by the Subject’s clinical state.

Relationship to study device or procedure should be rated as follows:

1. **None** (definitely not related): there is no relationship between study device or procedure and the event.
2. **Possible** (remote possibility, possibly, or probably related): the relationship between study device or procedure could exist if there is no contradicting evidence that can reasonably explain the Subject’s condition.
3. **Definite** (definitely related): the relationship between study device or procedure and event does exist and is confirmed upon further investigation by the investigator.

Pre-existing medical conditions or symptoms reported prior to device implantation are not to be recorded as AEs. In the event there is an exacerbation of the pre-existing medical condition or symptoms (due to the device or study related procedure), then an AE must be reported.

AEs are reported beginning from time of surgery until Subject participation has ended (study completed or Subject withdrawn). AEs must be followed to resolution or until the study completion or Subject withdrawal.

Subjects should be encouraged to report AEs spontaneously and may volunteer AE information at any time. At each evaluation, the investigator will determine whether an AE has occurred. If it is determined that an AE has occurred, the investigator should obtain all the information required to complete the appropriate AE form(s). If an event occurs at an outside institution, the investigator should attempt to obtain, if possible, required AE information to report to the Sponsor.

The investigator will record the nature, severity, treatment and outcome of the AE, and will determine their association to the device or the study procedure.

The following categories of AE severity are to be used:

1. **Mild:** awareness of a sign, symptom or event that is easily tolerated and transient in nature with minimal or no impairment to normal activity.
2. **Moderate:** moderate symptoms that are poorly tolerated, sustained, interfere with normal activity and require medical attention.
3. **Severe:** symptom(s) require intervention, and the activities of daily living are significantly altered.

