4.4 Data Collection

This section is applicable to individuals who have undergone screening, have signed an Informed Consent Document, and have otherwise been found eligible to participate in this study. This section details the pre-operative, operative, and post-operative management of Subjects.

In order to minimize the burden to patient and physician, patients will be enrolled at the physician's office, but will not be required to come back to the office for follow-up visits. The follow-up data to be collected as part of this study will be mailed or emailed to study

subjects by their study doctor at the selected time points (6 weeks, 3 months, 6 months, 1 year, 2 years, 3 years, 4 years, and 5 years). The patient will fill out the evaluation forms and then mail the forms back to their study doctor or complete them online. These forms may also be completed by phone with study staff; however an approved phone script must be used. Additionally, if the subject returns to the physician's office during a follow-up time point, the evaluation forms may be completed in person.

Zimmer Knee Creations will work with an electronic data capture (EDC) system developed to track all patient data for this observational cohort study. The EDC firm will complete the necessary diligence to ensure any platform selected meets the technical, reporting, data management, storage and security needs of the firm. Data collected on the CRFs will be included in the study database.

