5.2 Serious Adverse Events

A Serious Adverse Event (SAE) is defined as any untoward medical occurrence that:

1. Results in death
2. Is a life-threatening illness or injury
3. Requires inpatient hospitalization or prolongation of existing hospitalization
4. Results in persistent or significant disability/incapacity, or
5. Is a congenital anomaly/birth defect
6. Medical or surgical intervention to prevent life-threatening illness or injury or permanent impairment to a body structure or function.
7. Other serious (Important Medical Events). Report when the event does not fit the other outcomes, but the event may jeopardize the patient and may require medical or surgical intervention (treatment) to prevent one of the other outcomes.

For the purpose of this protocol, **any surgical intervention** is considered a serious adverse event. In case of death, all possible information available, such as autopsy or other post-mortem findings should be provided.

SAEs must be reported to the Sponsor as soon as possible and within 24 hours after the investigator first learns of the event. SAEs are reported to the respective Institutional Review Board (IRB) or Ethics Committee (EC), as per their respective requirements by the site.

6. Missed Follow-up Completion of Questionnaires

If a subject fails to complete the post-operative questionnaires at a follow-up time point, the site should continue to attempt follow-up of the subject through the five year study end point. The subject should only be considered Lost to Follow-Up and exited from the study under the conditions described in section 7.2. There should be at least three documented attempts to contact the subject to obtain follow-up data with any combination of an email reminder via OBERD, a phone call or an IRB approved subject follow-up letter.

7. Discontinuation of Subject Participation

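### Does the relatedness filter on adverse event reporting cover serious adverse events, and does the answer change any result the plan sets out?

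*Combined protocol and SAP*

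**What the plan says.** The filter appears twice. Section 5.1 states that "only AEs which are possibly or definitely related to the device or procedure will be reported to the sponsor", and the adverse event cell of Table 3 (Section 4.4.3) repeats it: "Only AEs which are possibly or definitely related to the device or procedure will be reported to the sponsor". The next sentence of that cell gives the timing for serious events: "Serious AEs must be reported as soon as possible and within 24 hours after the investigator first learns of the event". The cell then refers the reader to Section 5.

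Section 5.2 has its own version of the duty: "SAEs must be reported to the Sponsor as soon as possible and within 24 hours after the investigator first learns of the event". It lists seven criteria for seriousness, none of them tied to relatedness, and adds that "any surgical intervention is considered a serious adverse event".

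Relationship has three levels in Section 5.1: None, Possible and Definite. Possible is broad, covering "remote possibility, possibly, or probably related". For adverse events the investigator "will determine their association to the device or the study procedure". Section 4.5 (Data Analysis) does not mention adverse events, and no SAE table or listing is described anywhere.

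**The concern.** An SAE is a kind of adverse event. If the word only in Section 5.1 is taken at face value, an SAE rated None stays at the site. Read alone, Section 5.2 sends it to the sponsor within 24 hours. No sentence says which rule prevails, and up to 30 sites will apply them.

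Collecting safety data is a stated purpose of the study (Section 3). If some sites sent all SAEs and others only related ones, a pooled count would mix two reporting rules and could not honestly be titled as either. The sponsor would also not automatically hold the SAEs rated None at the filtering sites, should it later wish to review their attribution.

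**Working it through.** The documents give no figure to reproduce, so the check is to set the rules side by side and see which outputs depend on the reading.

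**Two readings.**

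| Event | A: filter covers SAEs | B: Section 5.2 has no condition |
|---|---|---|
| SAE rated Definite | sent | sent |
| SAE rated Possible | sent | sent |
| SAE rated None | not sent | sent |

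Only the last row differs. Reading A takes Section 5.1 as setting what is sent and Section 5.2 as setting when; the order of the two sentences in the Table 3 cell supports it. Reading B rests on the absence of any condition in Section 5.2.

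**Effect on a count.** Let R be the number of SAEs rated Possible or Definite, U the number rated None, and f the share of U that arises at sites on reading A.

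- All SAEs received = R + (1 − f)U. This runs from R + U at f = 0 down to R at f = 1.
- SAEs received and rated Possible or Definite = R for every f.

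The related-SAE count therefore does not depend on f. The shortfall in an all-SAE count is fU. The documents give neither f nor U, so fU has no numerical value. The approximate target of 1000 patients does not bound it either, because Section 3.3 sets no upper enrolment limit.

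**Which events rated None could be missed.** Section 5.2 gives eight grounds for an SAE (seven listed, plus any surgery).

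- Death: reaches the sponsor on the end-of-study form (Section 7.1). So do revisions that end participation.
- Any surgery: Form 4 has an item for surgical and non-surgical procedures, with no relatedness condition (Table 3), and "Data collected on the CRFs will be included in the study database" (Section 4.4). Secondary surgical intervention is also a separate evaluation parameter in the Synopsis.
- Intervention to prevent serious harm: covered by the same item where the intervention was a procedure, but not clearly where it was medical.
- Persistent disability: only the work and disability status item on Form 4.
- Life-threatening events, hospitalisation, congenital anomaly and other important medical events: no named route outside the adverse event form, unless the event was also fatal or involved a procedure.

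The exposed group is therefore mainly non-fatal, non-surgical SAEs rated None. It is narrowed further because an event thought only remotely related counts as Possible and is sent on both readings.

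**The case for a change.** The strongest case for a change is that the protocol should not leave this to inference. Parts of Section 5.2 point towards reading B: the last seriousness criterion is itself worded as an instruction to report, and full information is asked for on every death. Section 5.1 points the other way with an emphatic only. The other routes are weaker substitutes: Form 4 is completed by the subject at scheduled time points, the end-of-study form carries no 24-hour limit, and neither is described as recording seriousness or relationship. Section 8 does not collect deviations, so differing site practice might go unnoticed. A clarifying sentence would be cheap, and events never sent may be hard to recover.

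Much of this stands. The missing link is genuine, and a complete all-SAE count cannot be assured. Whether Section 5.2 means surgery on the treated knee only is likewise unstated. Three things limit what follows.

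- Divergence between sites is possible but not shown. Sites are trained on the study (Section 3.2), and the sponsor provides continuing education on data collection and reporting (Section 9.2).
- An SAE rated None need not be lost. Section 5.1 has the investigator record the event's nature, severity, treatment and outcome without a relatedness condition, so a site record should exist to query.
- Either clarification would remove the ambiguity, which marks this as unstated detail, not a wrong rule. Sending every unrelated SAE would add reporting work in a cohort that requires no follow-up visits (Section 4.4). It would still not guarantee completeness, since follow-up is largely by mail, email or phone and Table 3 names no hospitalisation item.

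**Conclusion.** The wording gap is confirmed, but it calls for no change to the plan. It affects only SAEs rated None, and among those mainly the non-fatal, non-surgical ones. No result that the protocol sets out is made wrong. A summary restricted to SAEs rated Possible or Definite is valid on either reading, and an analyst would title it that way and would not present the events received as all SAEs. Limiting sponsor reporting to related events is a defensible choice for a low-burden observational cohort; widening it to all SAEs is a trade-off for the sponsor to weigh.

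The size of any shortfall cannot be calculated from the documents. The conclusion assumes that the relationship rating travels with each reported event, and that an investigator's rating does not depend on how the site reads the reporting rule. It would be different if the plan promised a complete count or rate of all SAEs regardless of relationship; it does not.

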3. Study Design

This is a multi-center patient outcome observational cohort study intended to collect data on the short- and long-term safety and effectiveness of the SCP procedure. This observational cohort will become a repository of data reflecting patient experiences with the SCP procedure over time. Detailed patient demographic information (e.g., age, gender, location of defect, severity of symptoms, etc.) will be collected to determine the most suitable SCP patient population(s). The study duration is expected to be 10 years.

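### Section 5.1 uses inconsistent tests of relatedness, so a non-serious treated-knee event that underlying disease could also explain has no clear rating and may go unreported

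*Combined protocol and SAP*

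**What the plan says.** Section 3 describes a cohort "intended to collect data on the short- and long-term safety and effectiveness of the SCP procedure", and the synopsis lists safety among the evaluation parameters. Section 5.1 and Table 3 both restrict what is collected: "only AEs which are possibly or definitely related to the device or procedure will be reported to the sponsor".

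Section 5.1 then expresses relatedness in three ways.

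- **Narrative rule.** An event is related if a causal link "is at least a reasonable possibility, i.e. the relationship cannot be ruled out". A link cannot be ruled out when, in the investigator's judgment, "the effect follows a reasonable temporal association with the use of the device and/or is confirmed by the improvement of the effect" once the device is no longer used, "and/or the effect is not reasonably explained by the Subject’s clinical state".
- **Rating scale.** *None* is for events that are definitely unrelated. *Definite* needs confirmation by further investigation. *Possible* is labelled "remote possibility, possibly, or probably related", but the definition under that label reads "the relationship between study device or procedure could exist if there is no contradicting evidence that can reasonably explain the" subject's condition.
- **Worsening of pre-existing conditions.** Symptoms present before implantation are not adverse events. An exacerbation must be reported when it is caused by the device or a study-related procedure. This wording speaks of causation, not of possibility.

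**The concern.** In most studies relatedness is a label attached to an event already in the database, and it can be reviewed later. Here the rating decides whether a non-serious event reaches the sponsor at all. An event that is not rated *Possible* or *Definite* need not be sent, so it cannot be re-rated centrally or counted.

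The wording matters most for events of the treated knee. Every subject has a bone marrow lesion in that knee, so the underlying disease will often offer another explanation for a new symptom or sign. No comparator is described that would show an excess of such events. Up to 30 sites apply the text by investigator judgment, no central adjudication is described, and Section 8 says that protocol deviations are not collected. Sites could therefore read Section 5.1 differently without anyone seeing it. At stake are the completeness of the non-serious knee safety data and its comparability between sites.

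**Working it through.** The plan states no figure on this point, so there is none to reproduce. The check sets the tests side by side.

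**Inputs, all from Section 5.1.** Let T = reasonable temporal association, D = improvement when use of the device stops, and E = no other reasonable explanation. On the usual reading of and/or, one limb of the narrative rule is enough:

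- Narrative rule: related if T or D or E.
- *Possible*, with its *if* read as a defining condition: related if E.

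Using one E for both is a simplification. The narrative asks whether the subject's clinical state explains the effect. The scale asks whether contradicting evidence explains the subject's condition.

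**All combinations.** T, D and E give 2 × 2 × 2 = 8 cases. The narrative rule calls 8 − 1 = 7 related. The *Possible* definition calls 4 related (those with E). They disagree in 7 − 4 = 3: T alone, D alone, and T with D, each without E.

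**Setting D aside.** Section 2 says that the filler hardens within the lesion, so stopping use of the device will seldom be an available test. Four cases remain:

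| T | E | Narrative rule | *Possible* definition |
|---|---|---|---|
| yes | yes | related | met |
| yes | no | related | **not met** |
| no | yes | related | met |
| no | no | not related | not met |

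The one disagreement is the event that is well timed but could also be explained by the disease.

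**Placing that event on the scale.**

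- *None*: does not fit, because the event is not definitely unrelated.
- *Definite*: does not fit, because nothing confirms the link.
- *Possible*, by its definition: fails if the disease explanation counts as contradicting evidence.
- *Possible*, by its label: fits, since a remote possibility is enough.
- Worsening clause, if the event is an exacerbation: reportable only if caused by the device or procedure.

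**Other reading of and/or.** If it means that all three limbs are needed, the narrative rule calls 1 of 8 cases related and the definition still calls 4. They again disagree in 4 − 1 = 3 cases, with the narrative now the stricter. Neither reading makes the passages agree.

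These are counts of logical cases, not event rates.

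**Direction.** If p is the true rate of such events and r the fraction that sites report, the observed rate is p × r, with r no greater than 1. Any loss is therefore downward. The documents give neither p nor r.

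**The case against.** The strongest reply is that the labels alone work. Anything not definitely unrelated is at least a remote possibility, which matches the cannot-be-ruled-out rule. The definition says *if*, not *only if*, and an available disease explanation is not necessarily evidence that contradicts a device link. This stands as far as it goes: an investigator who relies on the label can rate the event *Possible* and report it. It shows that loss is not certain. It does not remove the conflict, because another investigator who relies on the definition has textual support for the opposite rating.

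Three stronger readings are tempting, and the documents do not support them.

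- *Knee deterioration in general drops out of the safety data.* Section 5.2 treats any surgical intervention as serious and puts no stated relatedness condition on serious events. It also covers hospitalization, significant disability and other important medical events. Form 4 collects medications, surgical and non-surgical procedures, VAS pain and IKDC from all subjects, so many events leave a partial trace. One doubt remains: neither Section 5.1 nor Table 3 says whether the related-only filter also limits serious events.
- *The conflict grows in years 2 to 5 as timing becomes less persuasive.* With T absent and D set aside, both tests reduce to E and agree. Late events lost in this way are lost under the narrative rule itself.
- *Every treated-knee event must therefore be reported.* Related-only reporting is a deliberate rule, stated twice, in a design that Section 4.4 says is meant to limit burden. One may debate it, but a conflict of wording does not overturn it.

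**Conclusion.** The concern holds in limited form. Section 5.1 does not apply one test of relatedness, and *Possible* disagrees with its own label. The events exposed are mainly non-serious, non-surgical events of the treated knee that are temporally associated with the procedure and could also be due to the underlying disease. These may go unreported, depending on how each site reads the text. That would bias the reported adverse event rate downward and make it differ between sites for reasons unrelated to safety.

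The size cannot be estimated: the documents give no event rates and nothing on how sites would divide between the readings, so any percentage would only return the assumptions put in. The conclusion assumes that and/or is satisfied by one limb and that some investigators will treat a disease explanation as contradicting evidence. It is worth correcting because the change is small and an event never sent to the sponsor cannot be recovered at analysis.

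**What to change.** Make all three parts of Section 5.1 apply the same test.

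1. Define *Possible* as any event whose relationship to the device or procedure cannot be ruled out, even when the subject's condition offers another explanation.
2. Keep *None* for events where a relationship is excluded.
3. Reword the worsening clause so that an exacerbation is reportable when it is rated *Possible* or *Definite*, matching the reporting rule. If this clause is left alone, a conflicting test remains for the very events that look like disease progression.

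The related-only reporting rule can stay as it is. The cost is a protocol wording change, site retraining, some additional adverse event forms, and a somewhat higher reported adverse event rate.

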4.4.1 Preoperative Procedures

Prior to surgery, the data in Table 1 must be collected for each enrolled Subject.

Table 1: Preoperative Data Collection

| Form 1—Medical History | |
|--------------------------------|---|
| Evaluation | Details of Evaluation |
| Enrollment Checklist | Authorized medical personnel will verify subject eligibility. |
| Patient Demographics | Authorized medical personnel will collect basic demographics from the preoperative time period. |
| Knee Related History | Authorized medical personnel will collect previous/current treatments and previous/current medications (prescription drugs) for the affected knee, as well as previous surgical treatments. |
| Concomitant Medical Conditions | Authorized medical personnel will collect medical conditions from the preoperative time period. |
| Current Medications | Authorized medical personnel will collect current medications (prescription drugs) not related to the affected knee. |

| Form 2—Pre-Operative Clinical Evaluation | |
|---|---|
| Evaluation | Details of Evaluation |
| VAS—Knee Pain | Each of the questionnaires should be completed by the Subject. It typically takes 5-10 minutes per questionnaire to complete. |
| Length of Painful Symptoms | |
| Work/Disability Status | |
| IKDC | |
| VR-12 Health Survey | |

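### Section 5.1 sets two different thresholds for worsening of pre-existing symptoms, so possibly related worsening of knee pain can be left out of the adverse event data

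*Combined protocol and SAP*

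**What the plan says.** Section 5.1 contains four statements that bear on a knee that is worse after the procedure.

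- The AE definition includes "or change or worsening of a pre-existing medical condition) in a patient, which may or may not have an association with the" device.
- Reporting is then filtered: "only AEs which are possibly or definitely related to the device or procedure will be reported to the sponsor". Table 3 in section 4.4.3 repeats this filter.
- Relatedness turns on whether a causal relationship "is at least a reasonable possibility, i.e. the relationship cannot be ruled out". One of the and/or criteria offered is that "the effect follows a reasonable temporal association with the use of the device". The grade Possible runs from a remote possibility up to probably related, provided nothing else reasonably explains the subject's condition.
- For baseline complaints there is a separate rule: "Pre-existing medical conditions or symptoms reported prior to device implantation are not to be recorded as AEs". The exception is that, if there is an "exacerbation of the pre-existing medical condition or symptoms (due to the device or study related procedure), then an AE must be reported".

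Knee pain VAS and IKDC are completed before surgery (Form 2, section 4.4.1) and at eight time points from 6 weeks to 5 years (Form 4, section 4.4.3). Form 2 also asks for "Length of Painful Symptoms". The synopsis lists safety as one evaluation parameter, glossed as adverse events, and lists VAS and IKDC as separate parameters. Section 4.5 mentions covariate analyses of post-operative outcomes and no safety summary.

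**The concern.** Form 2 asks every subject how severe the knee pain is and how long it has lasted, so knee pain is the expected pre-existing symptom in this cohort. The special rule for pre-existing symptoms therefore falls on the harm most relevant to a procedure on a painful knee, namely that the knee hurts more afterwards.

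If that rule is stricter than the general one, the AE data depend on which sentence a site applies. With about 30 sites, the same clinical picture could be an AE at one and not at another. Section 3 makes short- and long-term safety a stated purpose, so this affects what the study can say on one of its own aims. The scores that would show the worsening are collected, but nothing directs anyone to look at them for safety.

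**Working it through.** No arithmetic applies: the plan gives no figure on this point. The check sets the two rules side by side for a subject with knee pain before surgery.

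| State of the knee after surgery | General rule (definition plus reporting filter) | Exacerbation sentence, read literally | Same result? |
|---|---|---|---|
| Pain unchanged | No worsening, no AE | Not recorded | Yes |
| Worse, rated Definite | AE, reported | AE must be reported | Yes |
| Worse, rated None | AE by definition, not reported to the sponsor | No AE required | Yes, for the sponsor's data |
| Worse, rated Possible | AE, reported | No AE required unless judged to be caused by the device or procedure | **No** |

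The conflict is confined to the last row. That row matters because the general threshold was evidently set low to capture such events: it asks only that a link cannot be excluded, whereas the exacerbation sentence asserts causation.

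Next, could worsening in that row reach the safety results by another route?

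1. *Surgery.* Section 5.2 treats any surgical intervention as a serious adverse event, so worsening that leads to an operation should be captured. The section does not say how that rule interacts with the relatedness filter. Worsening managed without surgery is not covered.
2. *Investigator review.* Section 5.1 has the investigator decide at each evaluation whether an AE has occurred. Section 4.4 does not require office visits and lets forms be completed by mail, online or by phone. The questionnaire may then be the only signal, and no score triggers a review.
3. *The scores themselves.* VAS, IKDC and the AE item are all on Form 4, but no section compares the scores with baseline for safety, and the synopsis keeps them outside the safety parameter.

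Last, who has a baseline? Sections 3.1 and 4.1 admit patients who have already had the procedure, and section 4.2 allows no study activity before consent. A pre-operative score collected for the study cannot be assumed for these subjects.

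**The case against.** The strongest reply is that Section 5.1 gives only one relatedness scale. The parenthesis in the exacerbation sentence can be read as shorthand for that scale, and the sentence says when an AE must be reported, not that possibly related worsening is no AE. On that reading this is a wording ambiguity and nothing more. The reading is available, and investigators who adopt it would report such worsening. It does not remove the conflict, because the sentence does not refer to the general threshold and uses a stronger causal term. Even under the general threshold, Possible requires that nothing else reasonably explains the condition, and the underlying knee disease will often offer an explanation.

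There are also partial safeguards: AE determination at each evaluation, spontaneous reporting by subjects, medications and non-surgical procedures on Form 4, and secondary surgery as its own parameter. They stand, but none links a worse score to the safety results.

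Four stronger readings are tempting and are not supported.

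- A reader might infer that worsening counts only if the device caused it. The text also names the study-related procedure, so worsening attributed to the surgery must be reported.
- A reader might infer that the bar on recording baseline symptoms is itself a defect. It is not: unchanged pre-existing symptoms are properly not AEs.
- A reader might infer that the worsening is lost to the study. It remains in the outcome data; what it may be missing from is the AE data.
- A reader might infer that the AE table will show almost no worsening, or put a number on the shortfall. That would need the rate of worsening, the spread of relatedness ratings and the share of sites reading the sentence literally. The documents give none of these.

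**Conclusion.** The concern holds in limited form. Section 5.1 states two thresholds for the same event. They diverge for worsening of pre-existing symptoms that is possibly, but not definitely, related, and the practical gap is for worsening managed without surgery. Because safety is equated with adverse events and no section uses VAS or IKDC deterioration for safety, nothing in the plan closes that gap.

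The size cannot be estimated from the documents, and none is claimed. The conclusion rests on two assumptions: that some sites will apply the narrower sentence as written, and that knee pain is present before surgery in most subjects, as Form 2 implies. The change is worth making because it removes a source of attribution bias from a stated aim at small cost.

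**What to change.** 1. In section 5.1, replace the causal parenthesis in the exacerbation sentence with the section's own threshold: an exacerbation is reported when rated Possible or Definite for the device or the procedure. Leave the rule on unchanged baseline symptoms as it is.
2. In section 4.5, add a descriptive safety table giving, at each follow-up time point, the number and percent of subjects whose VAS or IKDC is worse than the pre-operative score by a margin fixed before the first analysis, regardless of relatedness rating. Restrict it to subjects with a pre-operative score and state how many lack one, for example those enrolled after the procedure.

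The cost is one phrase and one table from data already collected. The AE count may look somewhat less favourable. No comparator is described, so the table cannot separate harm from the device or procedure from the natural course of the knee disease, and it should say so.

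A mandatory investigator rating for every worsened form is not proposed. With about 1000 subjects and eight time points there could be up to 1000 × 8 = 8000 forms to screen, which sits badly with the stated wish in section 4.4 to keep the burden on patients and physicians low.
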